- 160mg loading dose followed by 80mg at Weeks 3 and 6
- 240mg loading dose followed by 160 mg at Weeks 3 and 6
- 560mg loading dose followed by 320mg at Weeks 3 and 6

The results of this study demonstrated that all doses of bimekizumab were well tolerated and there were no unexpected clinically relevant safety findings.

Infections (mostly nasopharyngitis) were the most commonly reported events in both the active treatment and the placebo group. None of the infections were considered serious or required treatment with antibiotics. Two subjects in the active treatment group experienced 1 local candida infection each (oropharyngitis and vulvovaginitis, respectively) that were nonserious and resolved with topical therapy. There was a reduction in mean neutrophil count in the active treatment group, although this drop was not clinically relevant and a clear relationship with dose or time was not evident. Some increases in liver function tests were reported, but none had a convincing relationship to exposure to study medication. The exploratory analysis showed clinically relevant improvement in activity of psoriatic arthritis and in skin involvement in those subjects with concomitant active psoriatic lesions.

Two additional studies of bimekizumab are ongoing. RA0123 is a Phase 2a, double-blind, randomized, placebo-controlled, multiple dose study to evaluate the safety, PK, pharmacodynamics, and efficacy of multiple doses of bimekizumab administered as add-on therapy to stable certolizumab pegol therapy in subjects with moderate to severe rheumatoid arthritis. UP0031 is a Phase 1 open-label, parallel-group, single-dose study to evaluate the relative bioavailability and tolerability of bimekizumab 160mg sc in healthy subjects.

Additional information on the clinical data for bimekizumab is available in the current version of the Investigator's Brochure (IB).

The current study, PS0011, is a 48-week extension study for eligible subjects who complete PS0010, a Phase 2b, randomized, double-blind, placebo-controlled, parallel-group, dose-ranging study in adult subjects with moderate to severe chronic plaque psoriasis. In PS0010, subjects will be randomized 1:1:1:1:1 to receive the following blinded study treatment regimens for a treatment period of 12 weeks:

- Bimekizumab 64mg administered sc Q4W
- Bimekizumab 160mg administered sc Q4W
- Bimekizumab 320mg loading dose administered sc at Baseline followed by 160mg dose administered sc Q4W.

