5 STUDY DESIGN

5.1 Study description

PS0011 is a multicenter, 48-week, double-blind, placebo-controlled, parallel-group, extension study to assess the long-term safety, tolerability, and efficacy of bimekizumab in eligible adult subjects with moderate to severe chronic plaque psoriasis who complete PS0010. At Week 12 of PS0010, all eligible subjects continuing into PS0011 will undergo the PS0010 Week 12 study assessments and any additional PS0011 Baseline assessments, and will then receive their first dose of bimekizumab or placebo in PS0011.

During the Treatment Period, subjects will attend study visits at the study site Q4W for study assessments and administration of bimekizumab or placebo by study site staff through Week 48. Any subject who does not achieve PASI75 response at Week 12 or later in PS0011 will be withdrawn from study treatment and will return to complete the Early Withdrawal Visit assessments. Following completion or early withdrawal from the 48-week Treatment Period, subjects will return for a SFU Visit 20 weeks after their last dose of bimekizumab or placebo in PS0011.

Subjects withdrawing early from the study will undergo the Early Withdrawal Visit assessments and will enter the SFU Period.

Subjects who received placebo or bimekizumab 64mg, 160mg, or 320mg loading dose + 160mg Q4W in PS0010 must achieve PASI90 response at Week 12 in PS0010 to enter the PS0011 extension study on the same treatment dose. Subjects who do not achieve PASI90 response at Week 12 in PS0010 while receiving placebo or bimekizumab 64mg Q4W will be assigned to receive bimekizumab 160mg Q4W on entering PS0011. Subjects who do not achieve PASI90 response at Week 12 in PS0010 while receiving bimekizumab 160mg or 320mg loading dose + 160mg Q4W will be assigned to receive bimekizumab 320mg Q4W on entering PS0011. Subjects who receive bimekizumab 320mg or 480mg Q4W in PS0010 will be assigned to receive bimekizumab 320mg Q4W on entering PS0011, regardless of their PASI90 response at Week 12 in PS0010.

A schedule of study assessments is presented in [Table 5–1](#).

A study schematic diagram of PS0011 is presented in [Figure 5–1](#).

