7.2 Treatments to be administered

During the Treatment Period, all subjects will receive bimekizumab or placebo Q4W administered sc (refer to [Figure 5–1](#) for further details).

Subjects who received placebo or bimekizumab 64mg, 160mg, or 320mg loading dose + 160mg Q4W in PS0010 must achieve PASI90 response at Week 12 in PS0010 to enter the PS0011 extension study on the same treatment dose. Subjects who do not achieve PASI90 response at Week 12 in PS0010 while on these treatments will be assigned to receive bimekizumab 160mg or 320mg Q4W at Baseline in PS0011 as follows:

- Subjects receiving placebo and bimekizumab 64mg Q4W in PS0010 will be assigned to bimekizumab 160mg Q4W in PS0011.
- Subjects receiving bimekizumab 160mg Q4W and 320mg loading dose + 160mg Q4W in PS0010 will be assigned to bimekizumab 320mg Q4W in PS0011.

Subjects who receive bimekizumab 320mg or 480mg Q4W in PS0010 will be assigned to receive bimekizumab 320mg Q4W on entering PS0011, regardless of their PASI90 response at Week 12 in PS0010.

The study medication is to be administered in the clinic by study site staff as 2 sc injections for all study treatments in PS0011. Suitable areas for sc injections are the lateral abdominal wall and upper outer thigh. Injection sites should be rotated, and injections should not be given into areas where the skin is tender, bruised, red, or hard.

The minimum time between doses should be no less than 24 days and no more than 32 days for Q4W dosing.

An IMP Handling Manual will be provided to each site containing instructions regarding drug preparation and dosing.

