14.2 General statistical considerations

No inferential statistical analyses are planned for this extension study. Instead, all variables will be presented using summary statistics. For categorical variables, counts and percentages will be displayed. For continuous variables, summary statistics will consist of the number of available observations, arithmetic mean, standard deviation, median, minimum, and maximum unless stated otherwise.

Because subjects entering PS0011 may or may not be continuing on the same dose as that received in PS0010, there are various combinations of treatment that could be received when considering both PS0010 and PS0011 together. For describing the summaries to be produced, treatment groups will be categorized as either the PS0011 treatment groups or PS0010/PS0011 treatment groups. These categorizations are outlined below.

PS0011 treatment groups

This refers to the study treatment assigned to the subject at the beginning of PS0011 and does not account for the treatment received in PS0010. The PS0011 treatment groups are as follows:

- Placebo
- Bimekizumab 64mg Q4W
- Bimekizumab 160mg Q4W
- Bimekizumab 320mg Q4W
- All Bimekizumab (optional – to be used only if specified)

PS0010/PS0011 treatment groups

This refers to the combination of the randomized treatment in PS0010 and the treatment assigned at the beginning of PS0011. Some groups have been combined where it is considered appropriate to do so. The PS0010/PS0011 treatment groups with descriptions are as follows:

- Placebo to Placebo – Subjects randomized to placebo in PS0010 who achieve PASI90 response at Week 12 of PS0010 and continue to receive placebo in PS0011.
- Placebo to Bimekizumab 160mg Q4W – Subjects randomized to placebo in PS0010 who do not achieve PASI90 response at Week 12 of PS0010 and are treated with bimekizumab 160mg Q4W in PS0011.
- Bimekizumab 64mg to Bimekizumab 64mg – Subjects randomized to bimekizumab 64mg Q4W in PS0010 who achieve PASI90 response at Week 12 of PS0010 and continue to receive bimekizumab 64mg Q4W in PS0011.
- Bimekizumab 64mg to Bimekizumab 160mg – Subjects randomized to bimekizumab 64mg Q4W in PS0010 who do not achieve PASI90 response at Week 12 of PS0010 and are treated with bimekizumab 160mg Q4W in PS0011.

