14.8 Determination of sample size

Up to 240 subjects are anticipated to enroll in PS0011. This number is based on the fact that 240 subjects are planned to be randomized in the feeder study, PS0010. The calculations to reach that sample size are outlined in the PS0010 protocol. As the primary objective of this study is to assess the long-term safety and tolerability of bimekizumab 320mg Q4W, the number of subjects anticipated is based on the number of subjects completing PS0010 and meeting eligibility requirements for PS0011.

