8.2 Other safety analysis

8.2.1 TEAEs

The following summaries will be provided by PS0011 treatment group and for the “All bimekizumab” group. In addition, all summaries of TEAEs “per 100 subject years” will display EAIR and EAER:

- Incidence of TEAEs – Overview
- Incidence of TEAEs per 100 subject years by SOC, HLT and PT
- Incidence of TEAEs per 100 subject years by SOC, HLT, PT and by Timing of Onset Relative to Anti-bimekizumab Antibody Status
- Incidence of TEAEs by Decreasing Frequency of PT
- Incidence of TEAEs by Maximum Severity, SOC, HLT and PT
- Incidence of Non-Serious TEAEs by SOC, HLT and PT
- Incidence of Non-Serious TEAEs Above Reporting Threshold of 5% by SOC and PT

The incidence of TEAEs per 100 subject years will also be summarized for PS0010 and PS0011 combined, where treatment emergence and exposure at risk are relative to the first dose of study drug in PS0010. In the case of a subject that switches study treatment when starting PS0011, exposure at risk to PS0010 treatment will end the day prior to the first PS0011 dose. Adverse events that occur on the PS0011 baseline visit date will be attributed to the PS0010 treatment.

The only exception to this definition is for the following types of events:

- Those that code to a High Level Term (HLT) of “Injection Site Reactions”
- Those which have been designated as an Injection Reaction on the AE CRF and do not code to a System Organ Class (SOC) of “Investigations”
- Those which have been identified as a hypersensitivity reaction or an anaphylactic reaction

When any of these events occur on the date of treatment switch at PS0011 Baseline, the AE will be attributed to the treatment initiated in PS0011.

All AE summaries will be ordered alphabetically by SOC and HLT within SOC and in terms of decreasing frequency for PT within HLT in the “All bimekizumab” treatment group.

For each subject and each AE, the worst severity recorded will be attributed and used in the by-severity summaries. Similarly, the worst causality (most related to treatment) will be attributed and used in the by-causality summaries. If severity or causality is missing, the worst case will be assumed.

If the intensity of an AE is unknown, it will be considered as severe. If the relationship to study drug is missing, it will be considered as related.

Additional tables will summarize TEAEs by relationship to study medication, TEAEs leading to withdrawal from the study, treatment-emergent SAEs, and deaths:

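### The combined PS0010+PS0011 TEAE tables (SAP 8.2.1) set columns of mainly Weeks 0-12 time (placebo, and 480mg if shown) beside columns of mainly later time (160mg, 320mg) without a split by period, so rates can differ with no treatment effect

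*SAP*

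**What the plan says.** SAP 8.2.1 plans two tables that pool the feeder study and the extension: all TEAEs and serious TEAEs, each with EAIR and EAER. In both, "treatment emergence and exposure at risk are relative to the first dose of study drug in PS0010". When a subject changes treatment at entry to PS0011, "exposure at risk to PS0010 treatment will end the day prior to the first PS0011 dose". From then on, time and events belong to the new treatment, apart from stated rules for events on the switch day. The old treatment keeps no 140-day tail.

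The protocol fixes who changes:

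- Protocol 7.2: "Subjects who receive bimekizumab 320mg or 480mg Q4W in PS0010 will be assigned to receive bimekizumab 320mg Q4W on entering PS0011". No 480mg is given in PS0011.
- Protocol 5.1: "Subjects who do not achieve PASI90 response at Week 12 in PS0010 while receiving placebo or bimekizumab 64mg Q4W will be assigned" to 160mg.
- Protocol 7.2, for those without PASI90: "Subjects receiving bimekizumab 160mg Q4W and 320mg loading dose + 160mg Q4W in PS0010 will be assigned to bimekizumab 320mg Q4W in PS0011".
- Protocol 14.2 keeps one placebo group in PS0011: placebo subjects "who achieve PASI90 response at Week 12 of PS0010 and continue to receive placebo in PS0011".

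The columns of the combined tables are not listed. SAP 8.2.1 introduces its summaries by PS0011 treatment group plus an all-bimekizumab group, and the PS0011 groups in SAP 3.6 do not include 480mg. No split by period and no caution about comparing columns is specified. The exposure summary in SAP 8.2.6 covers PS0011 only, so it would not show the mix.

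**The concern.** An exposure-adjusted rate puts columns on a common scale only if the rate does not depend on when the time was accrued. Here the switch rule ties treatment to period: some columns hold the feeder study's 12 weeks and others hold mostly the year that follows.

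The documents give reasons why the two periods might not be alike. Subjects who met a PS0010 withdrawal criterion cannot enter PS0011 (Protocol 6.2). PS0011 then removes subjects with related Grade 3 or higher AEs, with Grade 3 or higher laboratory values, or without PASI75 from Week 12 (Protocol 6.3), so later time comes from a selected group. Visits are every 4 weeks to Week 48. After that the next scheduled visit is the safety follow-up, 20 weeks after the last dose.

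The stake is how these tables would be read. In the PS0011-only tables the placebo group is placebo PASI90 responders alone and 480mg does not appear. A reader looking for a dose pattern or a placebo contrast in this study's report would turn to the combined tables.

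**Working it through.** **Inputs**

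- Subjects: "240 subjects are planned to be randomized in the feeder study, PS0010" (Protocol 14.8). Six regimens are listed in Protocol 2.2.1, so 240/6 = 40 per arm. Equal allocation is an assumption, because the ratio is printed with five 1s.
- PS0010: "blinded study treatment regimens for a treatment period of 12 weeks" (Protocol 2.2.1), so 84 days.
- PS0011: a completer has 24 injections, two per dose (SAP 7), and time at risk runs to last dose + 140 days (SAP 8.1.3).
- Not in the documents, so assumed: PASI90 rates, full roll-over and event rates.

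**The plan's own figure.** 24/2 = 12 doses; the last is at (12 - 1) x 4 = Week 44; 44 + 20 = 64 weeks, as in Protocol 5.1.1. Time at risk is 308 + 140 = 448 days. (Table 5-1 as extracted also marks dosing at Week 48, while Protocol 8.8 lists none. These need reconciling, but 68 weeks instead of 64 would not change the conclusion.)

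**Days per column**, with 50% PASI90 in the 64mg and both 160mg arms and no placebo responder:

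| Column | Weeks 0-12 | Later | Total | Weeks 0-12 share |
|---|---|---|---|---|
| Placebo | 40 x 84 = 3,360 | 0 | 3,360 (9.2 SY) | 100% |
| 480mg | 40 x 84 = 3,360 | 0 | 3,360 (9.2 SY) | 100% |
| 64mg | 40 x 84 = 3,360 | 20 x 448 = 8,960 | 12,320 (33.7 SY) | 27% |
| 160mg | 80 x 84 = 6,720 | (40+20+40) x 448 = 44,800 | 51,520 (141.1 SY) | 13.0% |
| 320mg | 40 x 84 = 3,360 | (40+40+40) x 448 = 53,760 | 57,120 (156.4 SY) | 5.9% |

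**Sensitivity of the shares**

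- PASI90 of 10% on 64mg with 20% on 160mg, up to 50% with 80%: later share of 160mg is 41,216/47,936 = 86% to 55,552/62,272 = 89%. Crossing the extremes widens this to 34,048/40,768 = 84% and 62,720/69,440 = 90%. For 320mg it is 43,008/46,368 = 93% to 64,512/67,872 = 95%.
- Placebo responders each add 448 later days: 1 of 40 gives 448/3,808 = 12% later; 2 of 40 give 896/4,256 = 21%; 4 of 40 give 1,792/5,152 = 35%.
- If 10% do not roll over and keep a 20-week tail from a Week 8 last dose, 480mg has 4 x 16 = 64 later weeks out of 544, or 12%.
- If PS0011 time averages 44 weeks, the later share is 81-85% for 160mg and 90-93% for 320mg (paired rates as above).

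**Effect on EAER.** Let k be the early rate divided by the later rate, the same for every treatment. With Weeks 0-12 share s, a column's rate relative to the later rate is 1 + (k - 1)s. For 480mg versus 320mg (s = 1 and 0.0588):

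- k = 1: ratio 1.00
- k = 1.5: 1.5/1.029 = 1.46
- k = 2: 2/1.059 = 1.89
- k = 0.67: 0.67/0.981 = 0.68

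For placebo versus 160mg at k = 1.5: 1.5/1.065 = 1.41 with no placebo responder. With 2 of 40, placebo has s = 0.789 and 160mg has s = 6,720/50,624 = 0.133, so the ratio is 1.395/1.066 = 1.31.

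**Effect on EAIR.** Its denominator stops at the first event (SAP 8.1.4). Suppose each subject's rate is constant in time with mean 2 per year, and varies between subjects as a gamma with relative variance 0.5. Then survival to t years is (1 + t)^-2, the expected time at risk is t/(1 + t), and EAIR = (2 + t)/(1 + t) per year. At 84 days (t = 0.230) this is 2.230/1.230, or 181 per 100 subject-years. At 448 days (t = 1.227) it is 3.227/2.227, or 145. The ratio is 1.25 from window length alone. With no variation between subjects it is 200 at both.

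**The case against.** The strongest reply is that nothing here shows the rates will differ. That stands. Neither document gives a time trend in AE rates; with a constant rate EAER is equal in every column, and 1.46 and 1.89 are the assumed multipliers after about 6% dilution. A reader might infer that 480mg will be made to look worse than 320mg, but if rates rise with time the distortion runs the other way.

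Four other stronger readings are tempting and are not supported:

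- *The 480mg column is a fact.* It is an inference. Attribution to the PS0010 treatment makes sense only if those treatments have columns, but the SAP does not list them.
- *Placebo is purely Weeks 0-12.* That holds only with no placebo PASI90 responder, and the design provides for such responders to stay on placebo.
- *Follow-up has no AE prompt.* Protocol 9.1.2 requires a prompt at each visit, and the safety follow-up visit records AEs. Only interim visits are missing.
- *Later time means late exposure to drug.* Placebo switchers start bimekizumab in PS0011, so time within 12 weeks of first bimekizumab is (6,720 + 3,360)/51,520 = 20% of the 160mg column, not 13%.

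It is also fair to say that these tables are supplementary and descriptive, that no inferential analysis is planned (Protocol 14.2), and that PS0010 has its own reporting. This limits the consequence, but rates printed side by side are still read as comparisons.

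**Conclusion.** The imbalance follows from the switching and cut-off rules; its exact size rests on 40 per arm, full roll-over, completion and assumed PASI90 rates. The contrast between placebo or 480mg and the two larger columns survives every variation tried. What is established is that unsplit rates can be shifted by period, in either direction, and that EAIR can also be shifted by window length when risk varies between subjects. A shift in the actual data is not established.

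The primary safety analysis (SAP 8.1.6) uses PS0011 time and PS0011 groups only and is not touched. This is a worthwhile, inexpensive improvement to two supplementary tables, not a flaw in the main result.

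**What to change.** In SAP 8.2.1, for both combined tables:

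1. List the columns, and say whether 480mg is one of them and where its time goes if not.
2. Present EAIR and EAER split at the first PS0011 dose (PS0010 Weeks 0-12; PS0011 time at risk), each with its own time at risk.
3. State whether a subject with the event in Weeks 0-12 is at risk again for the later-period EAIR.
4. State that placebo and 480mg are compared with other doses only within Weeks 0-12, where each randomised arm has about 40 x 84/365.25 = 9.2 subject-years.
5. If a pooled table is kept, footnote each column's share of Weeks 0-12 time.

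This needs SAP wording and extra table layouts, and no new data. The drawback is fewer events per cell, most noticeably for serious TEAEs.

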5.4 Rationale for study design and selection of dose

PS0011 is a 48-week, double-blind, placebo-controlled, parallel-group extension study for eligible subjects who complete PS0010, a Phase 2b, randomized, double-blind, placebo-controlled, parallel-group, dose-ranging study in adult subjects with moderate to severe chronic plaque psoriasis. Because some PS0010 subjects may have severe disease, the treatment in PS0011 provides more time to respond to a potentially efficacious treatment. PS0011 also provides an opportunity for nonresponding PS0010 placebo subjects to receive bimekizumab. This study will allow the collection of further data on the long-term safety, tolerability, and efficacy of bimekizumab in this subject population.

The PS0011 design (Figure 5–1) allows PASI90 responders in PS0010 to continue their dose in PS0011, thus permitting these subjects to remain on the dose that resulted in this response after 12 weeks of initial treatment in PS0010. It also provides an opportunity for an increased dose among PS0010 nonresponders (ie, <PASI90). PASI90 was selected as the response criterion in PS0010 to ensure that a sufficiently high efficacy response was achieved. This type of dose escalation for those who do not achieve a desired response after 12 weeks is common in clinical practice.

Regardless of PASI90 response at Week 12 of PS0010, subjects who received the 2 highest doses of bimekizumab (320mg and 480mg Q4W) in PS0010 will begin PS0011 on the 320mg Q4W dose. For those subjects who do achieve PASI90 response, this will allow a continuation of the PS0010 dose for subjects initially receiving 320mg Q4W and a dose down for subjects originally randomized to the 480mg Q4W dose. Because bimekizumab 480mg Q4W is the highest dose evaluated in PS0010 and because it requires 3 injections, it will be of interest to evaluate whether these subjects can maintain response in PS0011 with the lower 320mg dose, allowing the blind to be maintained with the use of only 2 injections at each study administration visit.

To protect against the possibility of exposing subjects to an ineffective treatment for extended periods of time, subjects across all treatment groups who have not achieved PASI75 response at Week 12 or later in PS0011 will be withdrawn from study treatment. Because this withdrawal decision is based strictly on the PASI response and not on the original study treatment, it can be done in such a way that will not unblind subjects or Investigators.

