 - Subjects may remain in the study if the event is transient. If a subject has a Grade 2 laboratory abnormality, a retest is required within 1 to 2 weeks at a scheduled or unscheduled visit. If the repeat value is below Grade 2, the subject may receive the next scheduled study treatment. If the value on the repeat is still Grade 2 or above, a second repeat test must be performed and results made available prior to the next scheduled study treatment. If this second repeat value is still Grade 2 or above, the subject must be withdrawn.
10. Subject has active suicidal ideation as indicated by a positive response (“Yes”) to questions 4 or 5 or to the suicidal behavior questions of the “Since Last Visit” version of the self-rated electronic Columbia-Suicide Severity Rating Scale (eC-SSRS). The subject should be referred immediately to a Mental Healthcare Professional and must be withdrawn from the study.
11. Subjects with a HADS-D score ≥ 15 must be withdrawn. Any subject who develops a HADS-D score of >10 during the study should be referred immediately to a Mental Healthcare Professional for further evaluation and potential withdrawal by the Investigator.
12. Subject does not achieve PASI75 at Week 12 or later following study treatment in PS0011.
13. Subject experiences an AE as described below:
 - Any CTCAE Grade 3 and above adverse event (AE) that is assessed as related to study drug in the opinion of the Investigator
 - If the event is deemed to be not related to study drug by the Investigator, the subject may remain in the study after approval by the Medical Monitor.
 - Any CTCAE Grade 2 event that is evaluated as related to study drug in the opinion of the Investigator, is persistent, and falls into any of the following System Organ Classes (SOCs): “Blood and lymphatic disorders,” “Cardiac disorders,” or “Vascular disorders.”
 - Persistent is defined as lasting 28 days or more, which spans at least 2 scheduled injections.

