14.3.2 Other safety analyses

Additional tables will summarize TEAEs by intensity and relationship to study medication, TEAEs leading to withdrawal from the study, treatment-emergent SAEs, and deaths. Other AE summaries to be included will be specified in the SAP. All AE tables will be presented by PS0011 treatment group (including the All bimekizumab group).

Extent of exposure to study medication in PS0011 will be summarized using descriptive statistics by PS0011 treatment group.

Change from Baseline in laboratory values, ECGs, and vital signs will be presented using descriptive statistics by PS0010/PS0011 treatment group. As these variables are summarized over time and the initial values can be impacted by the randomized treatment in PS0010, the presentation by PS0010/PS0011 treatment group is intended to provide perspective on the change in these values starting with the initial PS0010 randomization through the 48-week Treatment Period of PS0011. The table presentations will display descriptive statistics for the PS0010 Baseline followed by descriptive statistics for the observed, change from PS0010 Baseline, and change from PS0011 results by scheduled visit for PS0011.

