2.2 Study variable(s)

2.2.1 Safety variables

2.2.1.1 Primary safety variable

The primary safety variable is the incidence of treatment-emergent adverse events (TEAEs) adjusted by duration of subject exposure to treatment.

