- Incidence of TEAEs by Relationship, SOC, HLT and PT
- Incidence of Non-Serious TEAEs by Relationship, SOC, HLT and PT
- Incidence of Non-Serious TEAEs Above Reporting Threshold of 5% by Relationship, SOC and PT
- Incidence of Serious TEAEs per 100 subject years by SOC, HLT and PT
- Incidence of Serious TEAEs by Relationship, SOC, HLT and PT
- Incidence of TEAEs Leading to Discontinuation by SOC, HLT and PT
- Incidence of TEAEs Leading to Death by SOC, HLT and PT
- Incidence of TEAEs Leading to Death by Relationship, SOC, HLT and PT

The incidence of serious TEAEs per 100 subject years will also be summarized for PS0010 and PS0011 combined, where treatment emergence and exposure at risk are relative to the first dose of study drug in PS0010. In the case of a subject that switches study treatment when starting PS0011, exposure at risk to PS0010 treatment will end the day prior to the first PS0011 dose. Adverse events that occur on the PS0011 baseline visit date will be attributed to the PS0010 treatment. The only exception to this definition is for the following types of events:

- Those that code to a High Level Term (HLT) of “Injection Site Reactions”
- Those which have been designated as an Injection Reaction on the AE CRF and do not code to a System Organ Class (SOC) of “Investigations”
- Those which have been identified as a hypersensitivity reaction or an anaphylactic reaction

When any of these events occur on the date of treatment switch at PS0011 Baseline, the AE will be attributed to the treatment initiated in PS0011.

The following by-subject listings will be provided:

- All serious TEAEs
- All TEAEs leading to discontinuation of study treatment

- All death data
- All TEAEs and all non-TEAEs
- All treatment-emergent adverse drug reactions
- All AEs of special monitoring (AESM).

The following are AESM that require special statistical analyses:

1. Serious infections, opportunistic infections including TB and fungal infections

Serious infections will be identified based on MedDRA classification (SOC “Infections and infestations”) using the “Any SAE” table. A separate table does not need to be produced to summarize these events.

Fungal infections will be summarized in a stand-alone table which presents EAIR and EAER. The table will include all TEAEs which code into the high level group term (HLGT) of “Fungal infectious disorders”.

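### TEAEs leading to discontinuation have no planned exposure-adjusted rate, so their percentages are not comparable between PS0011 columns if PASI75 withdrawal differs

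*SAP*

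**What the plan says.** SAP 2.2.1.1 states that "The primary safety variable is the incidence of treatment-emergent adverse events (TEAEs) adjusted by duration of subject exposure to treatment". SAP 8.2.1 then sets the rule for the tables: "all summaries of TEAEs “per 100 subject years” will display EAIR and EAER". In its list of additional tables, one entry is "Incidence of Serious TEAEs per 100 subject years by SOC, HLT and PT". Another, without that label, is "Incidence of TEAEs Leading to Discontinuation by SOC, HLT and PT". Protocol 14.3.2 asks for summaries of "TEAEs leading to withdrawal from the study, treatment-emergent SAEs, and deaths" and states no exposure adjustment for them. The disposition summary in SAP 5.1 covers subjects who discontinued due to AEs but states no rate. That the discontinuation table will show only n and % is therefore read from the missing label; the SAP does not spell out its cells.

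Protocol 6.3, criterion 12, lists as a reason for withdrawal: "Subject does not achieve PASI75 at Week 12 or later following study treatment in PS0011". Protocol 5.4 says that "subjects across all treatment groups who have not achieved PASI75 response at Week 12 or later in PS0011 will be withdrawn from study treatment".

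Under the assignment rules (Protocol 5.1 and 14.2), the PS0011 placebo and 64mg columns hold only PS0010 PASI90 responders. The 160mg column holds placebo and 64mg non-responders together with PASI90 responders to the two 160mg regimens. The 320mg column holds non-responders to the 160mg regimens and everyone from 320mg and 480mg, whatever their response.

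**The concern.** Tolerability is part of the primary objective, and stopping drug because of an AE bears on it directly. A subject taken off treatment for lack of efficacy can no longer stop treatment for an AE. Each efficacy withdrawal therefore removes time in which the event could occur, while the subject stays in the denominator of the crude percentage.

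If the share withdrawn under the PASI75 rule is similar in all columns, the percentages remain comparable. If it differs, two columns with the same underlying rate of AE discontinuation will show different percentages, and the column with more efficacy withdrawals will show the lower one. Because the columns are formed by selecting on PS0010 response, equal withdrawal cannot be taken for granted.

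**Working it through.** **Inputs from the documents.** 24 expected injections for a completer (SAP 7). Duration of exposure = last dose − first dose + 28 days (SAP 8.1.2, eq 4). Exposure at risk = last dose − first dose + 140 days (SAP 8.1.3, eq 7). PASI75 rule from Week 12 (Protocol 6.3).

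**Check on the schedule.** Doses at Weeks 0, 4, …, 44 are 12 visits, and 12 × 2 = 24 injections, as the SAP states. Week 44 + 20 weeks = 64 weeks, which matches the maximum duration in Protocol 5.1.1.

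**Time on drug.**
- Completer: 44 × 7 + 28 = 336 days.
- Week 12 failure: PASI is assessed before dosing, so the last dose is at Week 8, and 8 × 7 + 28 = 84 days, a quarter of 336.

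**Assumptions (not in the documents).** The hazard of AE discontinuation while on drug is h per 100 subject-years, constant and equal in all columns. A share f of the column fails PASI75, all at Week 12.

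**Crude percentage.** With λ = h/100 per year:

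crude = (1 − f)(1 − exp(−λ·336/365.25)) + f(1 − exp(−λ·84/365.25))

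At h = 10 the two risks are 8.79% and 2.27%. At f = 30%: 0.7 × 8.79 + 0.3 × 2.27 = 6.83%.

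**EAIR** is events divided by subject-years to the event or to the end of the chosen period. The 8.1.3 period adds 140 − 28 = 112 days off drug for each subject without the event.

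| f | Crude % | Relative to f = 0 | EAIR, 8.1.2 time | EAIR, 8.1.3 time |
|---|---|---|---|---|
| 0% | 8.79 | 1.00 | 10.0 | 7.59 |
| 5% | 8.46 | 0.96 | 10.0 | 7.51 |
| 10% | 8.14 | 0.93 | 10.0 | 7.43 |
| 30% | 6.83 | 0.78 | 10.0 | 7.05 |
| 50% | 5.53 | 0.63 | 10.0 | 6.56 |

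- The relative loss hardly depends on h. At h = 5 the crude figures for f = 0, 5% and 30% are 4.50%, 4.33% and 3.49%. At h = 20, 30% failures give 13.11% against 16.81%, a ratio of 0.78.
- Later failure matters less. If the 30% fail at Week 24 (168 days on drug), the crude figure at h = 10 is 7.50%, 15% lower than 8.79%.
- Order can reverse. A column with a true rate of 12 and 30% failures shows 8.13%, below the 8.79% of a column with a true rate of 10 and none.
- The 8.1.3 time leaves part of the loss (7.05 against 7.59, 7% lower), because follow-up off drug cannot produce a discontinuation.

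**Sensitivity to the constant hazard.** Let the hazard be 12 per 100 subject-years for the first 84 days and 2 afterwards. Risk before Week 12 is 1 − exp(−0.12 × 84/365.25) = 2.72%. The later contribution is 1.33% at f = 0 and 0.7 × 1.33 = 0.93% at f = 30%.

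| f | Crude % | Subject-years on drug per subject | EAIR, 8.1.2 time | Rate before / after Week 12 |
|---|---|---|---|---|
| 0% | 4.06 | 0.893 | 4.54 | 12 / 2 |
| 30% | 3.66 | 0.693 | 5.27 | 12 / 2 |

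Here the crude figure is 10% too low in the high-failure column and the single EAIR 16% too high. Rates split at Week 12 agree in both columns.

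**The case against.** The strongest reply is that little is at stake. The primary variable is delivered with EAIR, 95% CI and EAER (SAP 8.1.6), and serious TEAEs and several special-monitoring topics also have rates. Protocol 14.3.2 asks for no adjustment of the discontinuation table, so nothing in the protocol is breached. Reasons for discontinuation (SAP 5.1), exposure by group (8.2.6) and a listing of these TEAEs are planned, so a reader would see a column with short exposure.

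The numbers are also small. Assuming equal allocation, 240/6 = 40 per PS0010 arm, so the 64mg column has at most 40 subjects. At h = 5, the gap between 0% and 30% failures is 4.50 − 3.49 = 1.01 points, or 0.4 of a subject in 40. The comparison is non-randomised and response-selected, and no inference is planned. All of this stands and limits the weight of the point. It does not supply the rate, its interval or its SOC and PT detail.

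A second reply is that EAIR is not neutral either. That also stands, as the sensitivity check shows: with all risk in the first 12 weeks the crude percentages would be equal and a single EAIR would mislead. It is a reason to split at Week 12, not to omit the rate.

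Three stronger readings are tempting and not supported:
- A reader might infer that the higher doses will look better tolerated. The rule is the same in every column and no PASI75 failure rates are given. The 160mg column includes placebo non-responders who had never received the drug, alongside 160mg responders, and the 320mg column is mixed too.
- A reader might call this the main tolerability comparison. The SAP places it among additional tables.
- A reader might extend it to the maximum-severity and relationship tables. Those events are still counted for 140 days after the last dose, so an efficacy withdrawal does not make them impossible, and the calculation here does not cover them.

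**Conclusion.** The point holds in conditional form. The discontinuation table lacks the rate that neighbouring tables carry, and if PASI75 withdrawal differs between PS0011 columns its crude percentages are not comparable. Under an equal, constant hazard with failures at Week 12, the relative understatement is about 4% for a 5-point difference in failure share and about 22% for 30 points. It is smaller if failures come later or if AE discontinuations cluster early. The failure shares and hazards are assumptions, so the size and direction by dose remain unknown. This is a low-cost improvement to a descriptive table, not an error in the primary analysis.

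**What to change.** In SAP 8.2.1, keep n and % in the discontinuation table and add EAIR with 95% CI by the method of 8.1.4. Count time from first PS0011 dose to onset of the event or to the end of duration of exposure under 8.1.2 (eqs 4–6). State this denominator in a footnote, since simply adding the per-100-subject-years label would bring in the +140-day time of 8.1.3.

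Show the overall row also split at Week 12, before and after PASI75 withdrawals begin, so that an early-weighted hazard does not distort the comparison. In the same footnote, say which event is counted: the SAP refers variously to withdrawal from the study, discontinuation, and discontinuation of study treatment.

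The cost is a few columns and one extra row from formulas and data already in the plan. The drawbacks are a wider table and wide intervals in small columns. For example, 2 events in 40 × 336/365.25 = 36.8 subject-years give an EAIR of 5.4 with an exact 95% interval of 0.7 to 19.6.
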